1.0 Objectives

1.1 Study Objectives

The specific aim of this prospective study is to determine whether local anesthetics prior to subacromial steroid injections reduce pain and consequently if they are cost-effective in the treatment for shoulder pathology.

Hypothesis: Patients undergoing subacromial steroid injections without local anesthetics will have significantly increased pain than those who do use anesthetics prior to undergoing the injections.

Standard of Care: Giving local anesthetics in addition to the steroid injection. Both of these treatment options are available to patients even if they are not undergoing the study.

1.2 Primary Study Endpoints

The primary endpoint is to determine whether local anesthetics prior to subacromial injections reduce pain, quantified on a 1-10 pain scale.

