7.2 Study Procedures

The study consists of one visit in clinic during their standard of care visit. Patients will be given information about the study and asked to participate. If eligible, based on inclusion and exclusion criteria, informed consent will be obtained at the time of the screening visit and the patient will be enrolled in the study.

After obtaining informed consent, the patient will be asked to rate their current pain on a visual 1-10 point scale before injection. They will then be randomized to one of three treatment groups. The study investigator will randomly draw a sealed envelope containing one of the three treatment groups. The sealed envelopes will be stored in a secure area within the clinic practice site. The subject will be randomized to one of three groups:

- Group A=Injection of 1 ml of 40 mg Kenalog combined with 4 ml of 1% lidocaine
- Group B=Injection of 1 ml of 40 mg Kenalog combined with 4 ml of 1% lidocaine after 2 ml in subcutaneous injection
- Group C=Injection of 1 ml of 40 mg Kenalog combined with 4 ml of 1% lidocaine after applying ethyl chloride spray for 3 seconds

The needle size will be standardized:

- 25 gauge needle for the subcutaneous lidocaine injection
- 21 gauge needle for the combined injection

Immediately after and ten minutes after the injection is completed, they will also be asked to rate pain on the same 1-10 visual scale.

No long-term follow-up will be conducted.

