8.2 Sample size determination

The primary endpoint is the change in visual pain scale from baseline (pre-injection) to follow up (0- and 10-minutes after injection). The study contains 3 groups:

- Group A=Injection of 1 ml of 40 mg Kenalog combined with 4 ml of 1% lidocaine
- Group B=Injection of 1 ml of 40 mg Kenalog combined with 4 ml of 1% lidocaine after 2 ml in subcutaneous injection
- Group C=Injection of 1 ml of 40 mg Kenalog combined with 4 ml of 1% lidocaine after applying ethyl chloride spray for 3 seconds

Comparisons will be made for the primary outcome between all 3 study groups: Group B vs. A; Group C vs. A; and Group C vs. B. Thus, we used a Bonferroni corrected Type I error rate for 3 tests to determine the sample size required for 80% power.

A total of N=50 patients per group (N=150 total) yields 80% power for a t-test conducted at the Bonferroni corrected Type I error rate of 1.7%, which holds the overall Type I error rate for the study at 5%, to detect a 2-point difference in pain scale changes between groups, assuming a common standard deviation of 3 points. The standard deviation was calculated after making a conservative assumption that visual pain scores would be uniformly distributed across 0-10.

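### The SD behind the 80% power is that of a single 0-10 score, but the endpoint is a change on a 1-10 scale, so the power depends on an unstated correlation

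*Combined protocol and SAP*

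**What the plan says.** **Scale collected.** Section 1.2 has the primary outcome "quantified on a 1-10 pain scale". In section 7.2 patients "rate their current pain on a visual 1-10 point scale before injection", and for the ratings immediately and ten minutes after it "they will also be asked to rate pain on the same 1-10 visual scale". No section gives the wording of the end points, or says whether the scale is a continuous line or whole numbers.

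**Scale assumed.** Section 8.2 obtains its SD by supposing that "visual pain scores would be uniformly distributed across 0-10", and describes that as conservative.

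**Quantity analysed.** Section 8.2 defines the primary endpoint as the change from the pre-injection rating to the ratings at 0 and 10 minutes, and section 8.3 puts that change into the one-way ANOVA. The sample size aims "to detect a 2-point difference in pain scale changes between groups", "assuming a common standard deviation of 3 points", with 50 patients per arm, 80% power and a Bonferroni level of 1.7% for each of three pairwise t-tests. No correlation between the ratings is given, and section 2.2 lists previous data as not applicable.

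**The concern.** Two features of the SD do not match the outcome. It was worked out for 0-10, while the form collects 1-10. It also describes one rating, while the analysis uses the difference between two.

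The SD is the only variability input to the sample size, and no earlier data support it. If it is too small for the change score, 50 per arm will not give 80% power for a 2-point difference. A non-significant result could then be read as showing that the anesthetic step makes no difference. That matters here because sections 2.1 and 2.3 say that finding no important effect could support dropping the anesthetic to save cost.

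**Working it through.** **Inputs.** From sections 8.1 and 8.2: 50 per arm, difference 2, SD 3, alpha 0.05/3 per comparison, t-test. Sidedness is not stated; two-sided is assumed. Power is from the noncentral t distribution with 98 degrees of freedom and noncentrality 2 / (SD × sqrt(2/50)) = 10/SD.

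**1. The plan's own figure.** With SD 3 the noncentrality is 10/3 = 3.33 and power is 81.3%. The smallest arm size for 80% is 49. The stated 80% at 50 per arm reproduces.

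**2. Where the SD comes from.** A continuous uniform score on 0-10 has SD 10/sqrt(12) = 2.887, which rounds up to 3. With 2.887 the t-test needs 46 per arm, and 3 × 46 = 138, the alternative sample size quoted in section 16.2. So the planning does rest on a single score over 0-10.

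**3. Effect of the range alone.** The SD of a uniform score is range/sqrt(12) if continuous, and sqrt((k² − 1)/12) for k whole-number categories. As in the plan, this step treats the single-score SD as the SD of the change.

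| Scale and scoring | SD | Power at 50 per arm |
|---|---|---|
| 1-10, continuous | 9/sqrt(12) = 2.60 | 91.9% |
| 1-10, whole points | sqrt(99/12) = 2.87 | 85.0% |
| 0-10, continuous | 10/sqrt(12) = 2.89 | 84.6% |
| Plan's value | 3 | 81.3% |
| 0-10, whole points | sqrt(120/12) = 3.16 | 76.5% |

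An SD of 3 covers both versions of the scale that section 7.2 collects.

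**4. Effect of analysing a change.** If the two ratings have the same SD and correlation rho, the SD of the change is SD × sqrt(2(1 − rho)). This equals the single-score SD only at rho = 0.5. The rho values below are assumptions chosen to show the range.

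| Assumed rho | SD of change, from SD 3 | Power at 50 per arm | Needed per arm for 80% |
|---|---|---|---|
| 0 | 4.24 | 47% | 96 |
| 0.3 | 3.55 | 65% | 68 |
| 0.5 | 3.00 | 81% | 49 |
| 0.7 | 2.32 | 97% | 30 |

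**5. Break-even correlation.** Solving the power formula for 80% at 50 per arm gives a largest allowable SD of change of about 3.045. Setting 2(1 − rho) = (3.045/SD)² gives:
- SD 3: (3.045/3)² = 1.030, so rho is about 0.48.
- SD 2.887: (3.045/2.887)² = 1.112, so rho is about 0.44.

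**The case against.** **The range mismatch does no harm to power.** This stands. The plan's arithmetic is right on its stated inputs, and on the 1-10 scale actually collected the uniform SD is below 3.

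A reader might still infer more from the mismatch. The documents do not support these readings:
- *That the SD belongs to a different instrument.* Only one visual pain scale is described, with its end points written inconsistently.
- *That the mismatch takes power below 80%.* The 76.5% case needs whole-point scoring on 0-10, which no section specifies. A figure of 71.3% arises only if the difference shrinks to 1.8 points while the SD stays at 3. If both shrink with the range (1.8 and 2.7), power is unchanged at 81.3%.
- *That a scale starting at 1 compresses change scores.* The anchors are not given and the form is not shown. If 1 is labelled as no pain, it serves as the zero point, and a constant shift cancels in a change.

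**Ratings by the same patient minutes apart may be well correlated.** They may, and at rho of 0.5 or more the stated power is met. But the plan neither states nor supports such a value. Section 7.1 says the pain of the injection itself is also to be assessed. A rating given immediately after the needle may partly reflect that pain rather than the shoulder pain rated at baseline, so a high correlation cannot be taken for granted.

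**A uniform distribution is a cautious choice.** That is a fair argument for the spread of one rating. It does not carry over to the difference between two ratings, whose SD can be smaller or larger depending on rho.

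**Conclusion.** The point holds in two parts of unequal weight. The inconsistent range is a real contradiction that needs correcting, but by itself it leaves power at 85% to 92% on the scale collected. The more important part is that section 8.2 uses a single-score SD for a change score and calls it conservative. The stated 80% is therefore conditional on a correlation of about 0.48 or more (about 0.44 if the unrounded 2.887 is used). Over an assumed rho of 0 to 0.7, power runs from 47% to 97%.

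This rests on a two-sided t-test, equal SDs at the two times, the plan's uniform model and a fixed 2-point difference. It does not show that the trial is underpowered, only that the plan gives no basis for saying that it is not.

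**What to change.** 1. In sections 1.2, 7.2 and 8.2 and on the data form, use one range with stated anchors (for example 0 = no pain to 10 = worst pain) and say whether it is scored in whole points or as a continuous line. If whole points on 0-10 are chosen, the uniform SD becomes 3.16 and section 8.2 must use it.
2. In section 8.2, drop the conservative label. Recompute the SD for the chosen scale and for the quantity analysed, state the assumed correlation and its basis, and give the power over a plausible range of rho.
3. Say whether the analysis uses the raw change or a baseline-adjusted score, and keep section 8.3 and its repeat in section 10.7 in line. With baseline adjustment and a linear relation, the residual SD is SD × sqrt(1 − rho²). This never exceeds the single-score SD, so the single-score figure would then be an upper bound.

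The cost is one form and a few wording changes, best made before enrolment. The drawback is that the restated power may be less favourable than 80%, or more patients may be needed.

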1.3 Secondary Study Endpoints

Not applicable

2.0 Background

2.1 Scientific Background and Gaps

Shoulder pain is a common problem that can be estimated to be prevalent in up to 15 percent of the patient population registered to general practices and is second only to back pain in patients seeking treatment for musculoskeletal issues in the primary care setting. As a common source of distress, shoulder pain contributes significantly to health care costs. In the US, it directly attributes \$7 billion to costs in the year 2000, with a mean cost per care episode of \$1667 and \$3011 for outpatient and hospital-based settings, respectively.

Rotator cuff disease due to impingement, tendonitis or bursitis is a frequent cause of shoulder pain and dysfunction. Initial treatment consists of a conservative approach of activity modification, oral nonsteroidal anti-inflammatory drugs (NSAIDs) and supervised physical therapy. However, if the patients' symptoms persist, subacromial injections of a local anesthetic such as lidocaine, and a corticosteroid may be indicated as a sequential treatment option.

The steroid injection itself can be a painful process, so administering a local anesthetic prior to the steroid injection is thought to mitigate pain or reduce possible discomfort during and immediately following the procedure. A survey of 835 rheumatologists found that 74.7 percent of those who trained after 1985 combined lidocaine and steroids for soft tissue and joint injections. Though there is evidence advocating for the benefits of combining local anesthetics and corticosteroids for the treatment of subacromial pathologies, it is not conclusive whether local anesthesia prior to steroid injections significantly enhances the pain relieving effect of steroids. Should local anesthesia not have a significant impact on the patient's pain intensity, then the use of corticosteroids alone could potentially result in reduced costs in care.

2.2 Previous Data

Not applicable

2.3 Study Rationale

Though there is evidence advocating for the benefits of combining local anesthetics and corticosteroids for the treatment of subacromial pathologies, it is not conclusive whether local anesthesia enhances the pain relieving effect of steroids. Should local anesthesia not have a significant impact on the patient's pain intensity as detected by self-assessment via pain scale, then the use of corticosteroids alone could potentially result in reduced costs in care.

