7.0 Study Design and Procedures

7.1 Study Design

The trial is a randomized, prospective study. Patients undergoing steroid injections will be randomized into three groups:

- Group A=Injection of 1 ml of 40 mg Kenalog combined with 4 ml of 1% lidocaine
- Group B=Injection of 1 ml of 40 mg Kenalog combined with 4 ml of 1% lidocaine after 2 ml in subcutaneous injection
- Group C=Injection of 1 ml of 40 mg Kenalog combined with 4 ml of 1% lidocaine after applying ethyl chloride spray for 3 seconds

Patients' pre and post-procedural pain as well as the pain of the injection itself will be assessed with a visual pain scale and the results will be analyzed for statistical significance.

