7.4.6.3 Preparation and Dispensing

The study drug will be prepared by an investigator following standard of care protocols. Subject randomization will be performed prior to dispensing of any study drugs. Once the needle is in the proper location, the solution of steroid will be injected slowly. A 2 mL solution of 1% lidocaine without epinephrine will be injected subcutaneously prior to the steroid injection if the subject is randomized into group B. If subject is in group C, ethyl chloride spray will be applied for 3 seconds prior the steroid injection.

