8.3 Statistical methods

A one-way analysis of variance (ANOVA) model will be used to test whether changes in pain scores differ by study group. The outcome variable for the model will be the change in pain scores, and the independent variables will be indicators of each study group. The overall F-test for study group will be used to determine whether study groups differ with respect to mean changes in visual pain scores. If the F-test is significant, then follow up tests comparing each set of groups will be conducted using the Bonferroni-adjusted Type I error rate of 1.7%.

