12.2 Potential Benefits to Others

The potential benefit may be a way to reduce healthcare cost by decreasing the over-utilization of unnecessary materials/procedures. The results of this study will guide future treatment decisions.

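### The cost argument rests on a null result and on steroid alone, but every group's injection contains lidocaine and no pairwise estimate is planned if the F-test is not significant

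*Combined protocol and SAP*

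**What the plan says.** - **Rationale.** Section 2.1 ends its argument with "pain intensity, then the use of corticosteroids alone could potentially result in reduced costs in care", and section 2.3 repeats it: "then the use of corticosteroids alone could potentially result in reduced costs in care". In both, the trigger is that anesthesia shows no significant effect.
- **Hypothesis.** Section 1.1: "Patients undergoing subacromial steroid injections without local anesthetics will have significantly increased pain than those who do use anesthetics prior to undergoing the injections". The same section makes cost-effectiveness part of the aim.
- **Arms.** Section 7.1: "Group A=Injection of 1 ml of 40 mg Kenalog combined with 4 ml of 1% lidocaine". Groups B and C receive the same mixture, preceded by a 2 ml subcutaneous injection or by ethyl chloride spray. Sections 7.2, 7.4.2 and 8.2 repeat these definitions.
- **Analysis.** Section 8.3, repeated in 10.7: "If the F-test is significant, then follow up tests comparing each set of groups will be conducted", at 1.7% each. Section 8.2 names B vs A, C vs A and C vs B as comparisons to be made and attaches no F-test condition.
- **Sample size.** Section 8.2 takes 50 per group as giving 80% power "to detect a 2-point difference in pain scale changes between groups, assuming a common standard deviation of 3 points".
- **Not stated.** The level of the F-test, what is reported if it is not significant, any confidence interval for a pairwise difference, and any margin for concluding that a step is unnecessary.

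**The concern.** Two things separate the cost argument from the trial.

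First, the regimen named as the potential saving is not studied. The arms differ only in what comes before a steroid–lidocaine mixture. If they turn out alike, that says something about skin anesthesia beforehand and nothing about removing lidocaine from the injection.

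Second, the cost argument applies when the result is null, and that is where 8.3 and 10.7 stop. A non-significant F-test can come with small observed differences that rule out a 2-point benefit, or with larger ones that do not. These support very different statements about cost, and only an estimate with its interval tells them apart.

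**Working it through.** **Inputs.** From 8.2: n = 50 per group, SD 3, difference 2 points, pairwise level 0.05/3 ≈ 1.7%. Assumed: two-sided tests, and an F-test at 5%. A true difference of 1.5 points is used as an illustration; the documents do not name it.

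**The plan's own figure.** The non-centrality is 2 / (3·√(2/50)) = 3.33. A two-sided t-test at 0.05/3 with 98 df then has power 81.3%, and 49 per group is the minimum for 80%. The stated 50 per group at 80% reproduces.

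**How often the F-test is non-significant when a difference exists.** Non-central F with 2 and 147 df, critical value 3.058, λ = n·Σ(μᵢ − μ̄)²/SD². With one group shifted by δ, Σ = 2δ²/3; with the third group midway, Σ = δ²/2.

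| True difference | Pattern | λ | P(F not significant) |
|---|---|---|---|
| 2 | one group shifted | 14.81 | 6.3% |
| 2 | third midway | 11.11 | 15.1% |
| 1.5 | one group shifted | 8.33 | 27.3% |
| 1.5 | third midway | 6.25 | 40.7% |

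**Precision of one contrast** (pooled SD, 147 df).
- 95% half-width: 1.976 × 3 × √(2/50) = 1.19. An observed benefit below 2 − 1.19 = 0.81 points excludes 2 points.
- 98.3% half-width, matching the 1.7% tests: 1.45. The cut-off becomes 2 − 1.45 = 0.55 points.

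**Largest observed difference that can still be non-significant.**
- Other two groups equal: √(3.058·2·9 / (50·2/3)) = 1.28. Upper 95% limit 2.47.
- Third group midway: √(3.058·2·9 / (50/2)) = 1.48. Upper 95% limit 2.67.

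So a non-significant trial can fall on either side of the 2-point planning difference.

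**How often each kind of null occurs** (simulation, 1,000,000 trials per scenario, 95% intervals).
- All groups equal: in about 7.5% of non-significant trials the interval for a given contrast does not exclude a 2-point benefit. For at least one of B−A and C−A it is about 13%.
- True B−A benefit of 1.5 points: 17% of all trials (B alone shifted, or B and C both shifted) to 28% (C midway) have both a non-significant F and an upper limit of 2 or more for B−A.

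**Sensitivity to the SD.** Section 8.2 derives its SD from scores spread uniformly over 0–10: 10/√12 = 2.89, rounded to 3. That is the SD of a score, whereas the endpoint is a change. If the scores before and after were independent, an assumption at the unfavourable end for non-negatively correlated scores, the SD of the change would be √2 × 2.89 = 4.08. The half-widths would then be 1.61 (95%) and 1.98 (98.3%), and the 7.5% would become about 31%.

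**The case against.** **The wording is loose, not wrong.** In 2.1 the preceding sentence is about anesthesia before the steroid injection, so steroid alone could mean no anesthetic step beforehand, which is Group A. Section 7.4.6.3 supports that usage: the Group B lidocaine "will be injected subcutaneously prior to the steroid injection if the subject is randomized into group B", where the steroid injection is the combined one. This largely rescues the hypothesis in 1.1. A reader might infer that the hypothesis cannot be tested; the documents do not support that, since B vs A and C vs A test it on this reading. It does not rescue the cost sentences. Section 2.3 never says the anesthetic comes beforehand, and both sections speak of combining anesthetic and steroid, so the literal words fit no arm. Section 12.2, which hopes for "a way to reduce healthcare cost by decreasing the over-utilization of unnecessary materials/procedures", shows that wording which fits the arms is already in the protocol.

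**The procedure is valid.** An F-test followed by Bonferroni tests is a conservative superiority analysis. That stands. A reader might also infer that the plan treats non-significance as proof of no benefit. It does not: no such rule appears, and the cost sentences are hedged.

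**The comparisons are not wholly gated.** Section 8.2 lists all three without condition. That stands, and it makes 8.2 inconsistent with 8.3 and 10.7. But 8.2 is the sample-size section and plans no estimate.

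**Intervals could be recovered.** If group means and SDs were published, a reader could compute them. True, but no section promises those summaries.

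**The size depends on the scenario.** At 2 points the F-test misses only 6–15%, and if the groups are equal about 92.5% of null trials already exclude 2 points for a given contrast. This is fair. The 17–28% rests on the illustrative 1.5 points.

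**Conclusion.** The point holds as a cheap improvement. On its literal wording, the cost argument in 2.1 and 2.3 refers to a regimen that no group receives, and the null result it depends on has no planned pairwise estimate. The weight lies in the missing estimate; the wording alone would be close to an editorial matter.

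The documents do not support the stronger conclusion that the superiority test is invalid or the sample size wrong: the F-test with Bonferroni follow-up is sound and the 50 per group reproduces.

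At SD 3 most null trials with truly equal groups would be informative about 2 points and a minority, about 7.5% per contrast, would not. That minority grows if the SD of the change exceeds 3. These figures assume 50 evaluable patients per group, approximately normal changes with a common SD, and a 5% F-test.

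**What to change.** 1. **In 8.3 and 10.7**, report B−A, C−A and C−B with confidence intervals whatever the F-test shows. State the level in advance: 95%, or 98.3% to match the 1.7% tests. Section 8.2 defines the change to both 0 and 10 minutes, so state which is primary, or give the intervals for each that is. Align 8.2 with 8.3 on whether the pairwise comparisons depend on the F-test.
2. **State that a non-significant F-test will not by itself be read as no benefit.** A margin, fixed and justified in advance, is needed only if the sponsor wants to claim that the pre-injection step is unnecessary.
3. **Reconcile the wording** on steroid alone in 2.1 and 2.3, and on injections without local anesthetic in 1.1, with the arms in 7.1 and 7.4.2. With the arms as written, limit the conclusion to no pre-injection step, subcutaneous lidocaine, or ethyl chloride spray, each before a combined steroid–lidocaine injection.

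The cost is a few sentences and three intervals per primary change score, from data already collected. No patients are added and the superiority objective is unchanged. The downside is that some null results will have to be reported as inconclusive.
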